## 1.0 PROTOCOL SUMMARY AND/OR SCHEMA

Translational studies in analgesic pharmacology: analgesic synergy in clinical pain. A phase 2 study comparing a single dose of a 1:1 combination of methadone and morphine with morphine alone in patients with post-operative pain.

The objective of this proposal is to compare the analgesic effects of a combination of morphine and methadone with morphine alone to determine synergistic activity of mu opioid analgesics in humans.

This is a randomized, double blind, parallel arm study (See Appendix 1).

We will administer a single dose of 1 mg of IV methadone plus 1 mg of morphine or 2 mg of IV morphine to patients one day after retroperitoneal lymph node dissection. We are planning for 70 patients to complete the study, 35 in each group.

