**IRB#: 05-025A(7)**

If the true difference between mean ratio B/A for morphine plus methadone vs morphine alone is .68 times the within-group standard deviation, then with 35 patients completing the study per arm there would be an 80% chance of a significant comparison with a two-sided t-test at  $p < 0.05$ .

The main analysis will be the analysis of covariance, using baseline pain as a covariate, and analyze time-to-first-rescue (the time from stopping PCA to first request for analgesic medication), and changes in pain intensity as secondary outcomes. We will also collect the information about the total dose of morphine received while on IV PCA and the dose of morphine received during the last hour before stopping the PCA and the time from stopping PCA to first request for analgesic medication to stratify subjects during analysis.

We are planning to review the data after 10 cases and may need to adjust the dose of morphine as well as morphine and methadone accordingly, by doubling the dosage. With the change of the dose, a new patient accrual will be started. The data for the initial opioid dose will be analyzed separately.

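### Three pre-dose continuous variables are assigned to undefined analysis strata, when they would serve better as continuous covariates in the main ANCOVA

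*Combined protocol and SAP*

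**What the plan says.** In Section 14.0 (Biostatistics), "The main analysis will be the analysis of covariance, using baseline pain as a covariate". Baseline pain is the only covariate named. The paragraph then gives three further variables a different job. Two are PCA morphine amounts, one cumulative and one for the final hour. The third comes with the stated purpose of the whole set: "the time from stopping PCA to first request for analgesic medication to stratify subjects during analysis". The paragraph gives no cut-points and no number of levels, does not say whether the three variables are crossed or taken singly, and names no model.

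The same paragraph also lists time from stopping PCA to first request as a secondary outcome.

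Section 1.0 sets the size: "We are planning for 70 patients to complete the study, 35 in each group". The power basis in Section 14.0 is a difference in mean B/A that "is .68 times the within-group standard deviation". The stated result, for a t-test that is two-sided at the 0.05 level, is that "with 35 patients completing the study per arm there would be an 80% chance of a significant comparison". Section 15.2 specifies simple randomization, so the design does not balance any of the three variables. Section 8.0 and Appendix 4 show that all three are already recorded.

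**The concern.** All three variables are settled before the open-label dose, and so before the blinded dose. Randomization codes are generated after consent, so the variables are strictly post-randomization. Treatment does not differ by arm until the second request, however, and allocation is blinded, so adjusting for them is legitimate.

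Cutting such variables into groups throws away part of what they say about the outcome. If they are crossed, it also spreads 70 patients over many cells, some of which may hold only one arm. Because the strata are undefined, several different analyses would all fit the text, and the choice could be made after the data are seen. At stake are a modest amount of power and the assurance that the adjusted result was fixed in advance.

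The two roles of time to first request are a separate defect. A time that ends before the blinded drug is given cannot measure that drug's effect.

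**Working it through.** **Inputs from the documents.** 35 completers per arm, 70 in total; difference 0.68 within-group SD; two-sided t-test at 0.05; simple randomization.

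**Assumed, because the documents are silent.** R2 of the three variables together for B/A: 0 to 0.3. Pairwise correlation: 0 to 0.5. Two or three levels per variable if stratified. The single degree of freedom for baseline pain is ignored throughout.

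**Step 1: the plan's own figure.** Noncentrality = 0.68 × √(35/2) = 2.845. With 68 df the critical t is 1.995 and power is 80.1%. The stated 80% reproduces.

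**Step 2: power with adjustment.** For continuous covariates, noncentrality = 2.845/√(1 − R2) on 65 df. For an additive median split of uncorrelated normal variables, R2 is first multiplied by 2/π = 0.637.

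| Assumed R2 | Continuous: noncentrality, power | R2 after split | Split: noncentrality, power |
|---|---|---|---|
| 0 | 2.845, 80.0% | 0 | 2.845, 80.0% |
| 0.1 | 2.999, 84.0% | 0.064 | 2.940, 82.5% |
| 0.2 | 3.180, 88.0% | 0.127 | 3.045, 85.1% |
| 0.3 | 3.400, 91.8% | 0.191 | 3.163, 87.6% |

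The advantage of continuous covariates over additive splits is about 1, 3 and 4 points at R2 of 0.1, 0.2 and 0.3.

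**Step 3: standard errors by simulation.** Step 2 leaves out the cost of chance imbalance in the covariates. Simulated trials (35 v 35, correlation 0.3, 2,000 runs) include it. Mean standard errors of the treatment effect, in SD units:

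| R2 | Unadjusted | Continuous | Additive medians | Crossed medians | Crossed tertiles |
|---|---|---|---|---|---|
| 0 | 0.238–0.239 | 0.244 | 0.244 | 0.252 | 0.296 |
| 0.1 | 0.237–0.238 | 0.230–0.231 | 0.233 | 0.241 | 0.283 |
| 0.2 | 0.238–0.239 | 0.218 | 0.226 | 0.233 | 0.269 |
| 0.3 | 0.238 | 0.204 | 0.216 | 0.223 | 0.255 |

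At R2 = 0 the price of three covariates is visible: simulated power is 77–78% against 79–81% unadjusted (Monte Carlo error about 1 point). The expected variance inflation for three covariates in 70 patients is 1 + 3/(70 − 3 − 3) = 1.047. Adjustment therefore breaks even where (1 − R2) × 1.047 = 1, at R2 of about 0.045.

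**Step 4: cell sizes.**
- One variable at a time, median split: 70/(2 × 2) = 17.5 patients per arm per stratum.
- Three variables crossed at the median: 2³ = 8 strata, 16 arm-cells, 70/16 = 4.4 patients on average. In simulation some stratum lacks an arm in about 10% of trials at correlation 0, 19% at 0.3 and 36% at 0.5.
- Three variables crossed at tertiles: 3³ = 27 strata, 54 arm-cells, 70/54 = 1.3 on average. Essentially every simulated trial has a one-armed stratum. On average 17 to 20 of the 70 patients sit in such strata and add nothing to a within-stratum comparison.

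**The case against.** The strongest reply is that the plan never says it will cross the three variables. A reader might infer from the text that stratifying necessarily leaves near-empty cells. The documents do not support that: one-at-a-time and additive strata have no such cells, and even crossed medians give no one-armed stratum in roughly 64% to 90% of trials. This part of the objection stands, and sparse cells are a risk of one permitted reading only.

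A reader might also infer that stratifying forfeits about 36% of the explained variance (1 − 2/π). That holds for uncorrelated normal variables in an additive split. With correlation 0.5 the loss is about 24%. The 2-hour removal rule truncates the third variable, so normality is doubtful too. The worst sparse-cell figure and the 36% loss also belong to different models (crossed and correlated, against additive and uncorrelated) and should not be added together.

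Third, the endpoint is B/A, in which each patient's response is divided by his own open-label response. That may already remove much of what these variables predict, leaving a small R2. This stands as a limit on the gain. It does not favour strata, which share the same R2 and were no more precise than continuous covariates in any setting simulated.

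**Conclusion.** The point holds in a moderate form. The plan assigns three already collected pre-dose continuous variables to an undefined stratification and leaves them out of the main ANCOVA. Continuous covariates are the better use. In the simulations they were more precise than every form of stratification tried at R2 of 0.1 or more, and at R2 = 0 they only tied with additive median strata.

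Against additive median splits the gain is about 1 to 4 power points for R2 of 0.1 to 0.3. Against no adjustment it is about 4 to 12 points by the Step 2 calculation. Against crossed strata it is larger, but the crossing is an assumption. All of these gains rest on an R2 that the documents do not give and on roughly linear effects. If the variables explain less than about 4.5% of the variance of B/A, adjustment brings no gain and costs up to about 2 power points.

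Two conclusions need no assumption. The stratified analysis cannot be reproduced from the text, and time to first request cannot serve as an outcome of a drug given later. None of this invalidates the primary comparison. It is an inexpensive improvement that should be made.

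**What to change.** In Section 14.0, replace the clause on stratifying with a statement, fixed before unblinding, along these lines: *The main ANCOVA of the B/A ratio will include baseline pain, total PCA morphine dose, PCA morphine dose in the final hour, and time from PCA stop to first request, the last three as continuous covariates. Any display by strata of these variables is descriptive.*

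Remove time from stopping PCA to first request from the secondary outcomes and keep it as a baseline variable only.

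The cost is two wording changes and 3 of 68 degrees of freedom. No new data or patients are needed. The one downside is the small loss of precision shown above if the variables turn out not to be prognostic.

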**IRB#: 05-025A(7)**

All participants must be registered through the Protocol Participant Registration (PPR) Office at Memorial Sloan-Kettering Cancer Center. PPR is available Monday through Friday from 8:30am - 5:30pm at [contact]. The PPR fax numbers are [contact] and [contact]. Registrations can be phoned in or faxed. The completed signature page of the informed consent form, the completed signature page of the Research Authorization and a completed Eligibility Checklist must be faxed to PPR.

During the registration process registering individuals will be required to answer specific eligibility questions and provide the following information:

Registering Individual	[Last, First Name]
Notice of Privacy Status	[Yes, No, N/A]
Research Authorization	[Date]
MSKCC IRB Protocol#	
Attending of Record (if applicable)	[Last, First Name]
Consenting Professional	[Last, First Name]
Informed Consent Date	
Participant's Full Name	[Last, First Name]
Participant MRN	

### **15.2 Randomization**

After meeting eligibility criteria, the patient will be assigned to the morphine/methadone combination arm or morphine alone arm randomly, using simple randomization. Randomization Codes will be generated by the Clinical Research Database (CRDB) in conjunction with the Department of Epidemiology and Biostatistics after signing the consent. Medications will be dispensed by the hospital pharmacy in a double-blind manner on the days of the study.

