## 4.2 Intervention

All patients will receive Patient Controlled Analgesia (PCA) with IV morphine as per routine post-operative analgesic care. The total amount of morphine available to patients will be equivalent to the standard amounts used after surgery. Informed consent will be obtained from all patients pre-operatively. The PCA settings will start in the recovery room at 1 mg/hour continuous infusion and 1mg every 10 minutes as needed, clinician activated boluses will be available, and the PCA will be titrated to pain control as needed.

The day after the surgery, the PCA will be stopped temporarily, and we will ask the patient to request pain medication as soon as he feels at least moderate pain (See Appendix 1). If two hours pass before a first request for pain medication is made, the patient will be removed from the protocol. During the period of the trial the doctor will have no other clinical or other responsibilities. A doctor will be available to monitor the time to the patients' request for pain medications, assess pain intensity and administer the drugs to replace the PCA promptly upon the patient's request. No more than 2 patients per doctor per floor will be enrolled on the same day.

Upon the first request for analgesia, immediately before administration of morphine 2 mg and every 10 minutes after administration of morphine 2 mg, we will record the patient's pain relief, pain intensity, respiratory rate, and side effects as reported by the patient. If four hours pass before a second request for pain medication is made, the patient will be removed from the protocol.

Upon the second request for analgesia, immediately before administration of the blinded study drug (1 mg of IV methadone plus 1 mg of morphine or 2 mg of IV morphine), every 10 minutes thereafter, and at the time of the third request for analgesia, we will record the patient's pain relief, pain intensity, respiratory rate, and side effects as reported by the patient.

Upon a third request for analgesia, the study is completed and the PCA will be restarted at the pre-study dose. If four hours pass before a third request for pain medication is made, the patient will be removed from the protocol.

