**IRB#: 05-025A(7)**

significant side effects in patients who have been already receiving morphine for over 12 hours.

Methadone, the 50/50 racemic combination of d-methadone and l-methadone, has been in widespread use for decades and has been studied extensively. There is no evidence of organ toxicity from chronic opioid use, including chronic methadone use (21). The main concern when using methadone for the treatment of pain is its long and unpredictable half-life which, with chronic administration, is associated with the risk of delayed opioid toxicity with side effects such as sedation, confusion and respiratory depression. For this reason methadone is generally viewed as a second line opioid, generally used after other opioids with a more predictable dose-response have been tried. This is a single dose study and therefore drug accumulation will not occur. Because of the low dose used, we do not expect toxic effects or significant side effects in patients who would be receiving morphine for over 12 hours by the time the study begins.

Preservative-free methadone and morphine combination (1 mg morphine+1 mg methadone) and parenteral morphine (2 mg of morphine IV) will be prepared, vialled and blinded by the MSKCC pharmacy. The methadone injection will be provided in single use vials containing 1 mg/ml, 0.5 ml, or 1 mg/ml, 2 ml. The morphine injection will be provided in vials containing 5 mg/ml, 1ml. Morphine and methadone are compatible for 7 days. Drugs will be dispensed by the pharmacy to the clinical investigator in a blinded fashion on the day of the study.

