### 13.0 CRITERIA FOR REMOVAL FROM STUDY

- Patients that develop complications after surgery resulting in: inability to use the PCA, inability to evaluate the patient or new pain beyond the post-surgical pain.
- Patients who require immediate post-operative opioid analgesia other than PCA morphine.
- Patients who require no analgesic medication 2 hours following the PCA being stopped.
- Patients who require no analgesic medication 4 hours following open label morphine 2 mg IV administration.
- Patients who require no analgesic medication 4 hours following the study drug (1 mg of methadone IV plus 1 mg of morphine IV or 2 mg of morphine IV).
- Patients that require new analgesic medications or analgesic adjuvants (including steroids) for the treatment of pain.

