**IRB#: 05-025A(7)**

**SYNERGY: Appendix 2: Inclusion and Exclusion Criteria**

PRE-OP ASSESSMENT FOR RANDOMIZATION

Date: \_\_\_/\_\_\_/\_\_\_\_\_

Inclusion criteria	
Scheduled for retroperitoneal lymph node dissection	
18-y-o or older	
English-speaking	
Informed consent signed	
Exclusion criteria	
Anesthesiologist disapproves morphine continuous	
H/o hypersensitivity to morphine or methadone	
H/o substance abuse	
H/o methadone treatment	
H/o opioid treatment for chronic pain	
H/o opioids within 1 month	
Creatinine clearance less than 50%	
Neurological or psychiatric disorder interfering with data collection (doctors discretion)- with comments (use additional sheet if necessary)	
Comments	

**Memorial Sloan-Kettering Cancer Center  
IRB Protocol**

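### Allocation is made before surgery, although patients can be removed up to the second analgesic request, so an all-randomised analysis of the primary ratio is not possible

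*Combined protocol and SAP*

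**What the plan says.** Section 15.2 ties allocation to two events, eligibility and consent: "After meeting eligibility criteria, the patient will be assigned to the morphine/methadone combination arm or morphine alone arm randomly, using simple randomization", and "Randomization Codes will be generated by the Clinical Research Database (CRDB) in conjunction with the Department of Epidemiology and Biostatistics after signing the consent". Both are settled before the operation. Section 4.2 says "Informed consent will be obtained from all patients pre-operatively". The Appendix 2 checklist is headed "PRE-OP ASSESSMENT FOR RANDOMIZATION", and its surgical item is only "Scheduled for retroperitoneal lymph node dissection".

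The blinded drug comes later. Under Sections 4.2 and 9.0 the PCA is stopped on the day after surgery. Every patient receives the same open-label morphine at the first request, and the randomised drug is given at the second.

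Section 13.0 lists removals that can take effect in between: post-operative complications, need for an opioid other than PCA morphine, "Patients who require no analgesic medication 2 hours following the PCA being stopped", and "Patients who require no analgesic medication 4 hours following open label morphine 2 mg IV administration". Its last item, new analgesics or adjuvants, can also fall in this window.

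Sections 12.0 and 14.0 define the primary outcome as area B (after the study drug) relative to area A (after open-label morphine). Sections 1.0 and 14.0 count only patients who complete: 70 in total, 35 per arm. No section gives an expected removal rate, a number to randomise, or an analysis set for patients who are randomised but never receive the blinded drug.

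**The concern.** A randomised comparison is best protected when the patients analysed are those randomised. Here the two groups differ by design, because the arm is assigned before several events that decide whether the patient can receive the assigned drug at all. Nothing in the design needs the arm to be fixed so early, since treatment is the same in both arms until the second request.

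The trial thus gives up the option of an intention-to-treat analysis of its primary outcome. Some of the removals are also judgements, such as whether a patient can be evaluated or has pain beyond the surgical pain. Made after allocation, they are harmless only while concealment holds. Made before allocation, they could not affect the comparison even if it failed.

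**Working it through.** **1. Order of events**

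| Moment | What happens | Source |
|---|---|---|
| Before surgery | Consent, eligibility checklist, randomisation code | 4.2, 15.2, Appendix 2 |
| After surgery | Removal for complications or a non-PCA opioid | 13.0 |
| Next day, PCA stopped | Removal if no request within 2 h | 4.2, 9.0, 13.0 |
| First request | Open-label morphine, same in both arms; area A starts | 1.0, 12.0 |
| After first request | Removal if no second request within 4 h | 4.2, 9.0, 13.0 |
| Second request | Blinded drug; area A ends, area B starts | 9.0, 12.0, 14.0 |

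The Appendix 4 form, used for the open-label dose, already has a field for a randomisation number. That fits early allocation but does not prove it, since the field could be filled in later.

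**2. Data available for a removed patient**

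- Removed before the first request: neither area A nor area B.
- Removed between the first and second requests: no area B.

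In both cases B/A cannot be computed, so an analysis of all randomised patients is not available for this outcome.

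**3. Can these removals depend on arm?** Until the second request the treatment is identical, and the study drug is blinded by the pharmacy. If blinding holds, removal is independent of arm. Patients who reach the blinded dose are then comparable between arms, as if randomised at that moment.

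**4. The plan's power statement** (Section 14.0: difference 0.68 SD, 35 completing per arm, two-sided 0.05)

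- Noncentrality: 0.68 × √(35/2) = 2.845.
- Normal approximation: Φ(2.845 − 1.960) = Φ(0.885) = 81.2%.
- Exact noncentral t: 80.1%, with 34.94, i.e. 35, per arm required.

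The stated 80% is reproduced. It refers to completers, so removals before the blinded dose do not alter it as long as accrual continues until 70 complete.

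**5. Numbers consented to treat 70.** The removal share f is an assumption, because the documents give none. Consented = 70/(1 − f), rounded up.

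| Assumed f | 70/(1 − f) | Consented | Not reaching the blinded dose |
|---|---|---|---|
| 10% | 77.8 | 78 | 8 |
| 20% | 87.5 | 88 | 18 |
| 30% | 100.0 | 100 | 30 |
| 40% | 116.7 | 117 | 47 |

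These counts are the same whether allocation is early or late. Under the current timing the last column holds randomised patients without a primary outcome. With allocation at the second request, it holds patients who were never randomised.

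**The case against.** The strongest reply is that nothing is biased. Pre-dose removals happen under identical, blinded treatment, so a comparison of all patients who received the blinded dose would already be valid. That stands, and it limits this point to the analysis set and to robustness.

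Several stronger readings are tempting, but the documents do not support them:

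- **Lost power or wasted patients.** If 70 were the number randomised, exact-t power would be 75.7%, 70.5% or 64.5% with 10%, 20% or 30% removed. But the plan counts 70 who complete. Later allocation saves no patients either, since the same 78 to 117 must be consented and followed to the second request.
- **Lost balance between arms.** Section 15.2 specifies simple randomisation, and Section 14.0 stratifies only at analysis. No balance is set in advance, so none can be lost.
- **Allocation on the study morning would do.** It would not: the 2-hour and 4-hour removals both come after the PCA is stopped.
- **Allocation immediately after consent.** Section 15.2 gives no interval. Pre-operative timing rests on that section together with Section 4.2 and the Appendix 2 heading. Some text just before the registration details was not available for this review; nothing that was available sets a later time.

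Removal for no request within 4 hours after the study drug is another matter. It can depend on arm, and moving allocation does not cure it. It affects this point only through the definition of the analysis set.

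**Conclusion.** The point holds as one of design and analysis set. Allocation precedes several removal steps that have nothing to do with the randomised drug, and the primary ratio does not exist for patients removed there. The plan is left with completers where a true all-randomised comparison could be had at little cost.

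Bias is not demonstrated, and the 80% power for 70 completers is correct. The size of the gap is unknown: 8 to 47 randomised patients without a primary outcome for every 70 treated, under assumed removal of 10% to 40%. The conclusion rests on reading Section 15.2 and Appendix 2 together as pre-operative allocation. The change is worth making, but the trial's validity does not hang on it.

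**What to change.** - **Section 15.2:** keep pre-operative consent and registration, but make allocation effective at the second request. The pharmacy supplies sequentially numbered blinded doses, and a number is consumed only when its dose is given.
- **Section 13.0 and the Appendix 2 title:** present the pre-dose removals as conditions for entering randomisation. No dose, time limit or rescue rule changes.
- **Section 14.0:** define the primary analysis set as all patients randomised at the second request. Include those with no third request within 4 hours. Appendix 5 already provides for their relief scores to 240 minutes, so the plan need only state how area B is closed for them. Section 9.0 describes such patients both as having completed the study and as removed from the protocol; those statements must be reconciled.
- **Reporting:** give the number consented, the number leaving before the second request with reasons, and the number randomised.

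If early allocation is kept, the minimum is to define the primary set as all patients given the blinded dose, report pre-dose removals by arm, and state the expected removals and the number to randomise.

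The cost is a wording amendment plus numbered doses. Section 5.0 already provides that "Drugs will be dispensed by the pharmacy to the clinical investigator in a blinded fashion on the day of the study" and states that the two drugs are compatible for 7 days. The downside is small: a blinded dose is prepared that may not be used, as is already the case.
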